Official title: Maximizing Use of Continuous Positive Airway Pressure in Stroke Rehabilitation Patients With Obstructive Sleep Apnea

NCT number: 02809430

Document date: March 10, 2019

Design: Single-arm, open-label study

Objectives: To assess the effectiveness of a multifaceted and intensive adherence program on 3month CPAP adherence and measures of stroke outcome (NIH stroke scale and Functional Independence Measure) among stroke patients undergoing inpatient rehabilitation (IPR)

Methods:

Eligible stroke patients (Table I) were enrolled and trialed auto-adjusting CPAP (4–20 cm H2 O; Dream Station, Philips Respironics) over a 3-night run-in period during IPR. Devices were interrogated for nightly usage, average pressure, and a residual apnea-hypopnea index (the respiratory events per hour of sleep). At the end of the run-in period, evidence of OSA was determined based on airflow resistance detected by the machine (see diagnosis of OSA below). Patients with evidence of OSA were eligible for CPAP treatment during IPR and after discharge from IPR. Nurses, respiratory therapists, sleep technologists, and clinical psychologists initiated the SCOUTS intensive CPAP adherence protocol during IPR emphasizing early CPAP tolerance, individual motivation (Table II) and support throughout the treatment period. The primary end point was CPAP adherence over 90 days from CPAP initiation, defined as \geq 4 hours of use on \geq 70% of days. Secondary efficacy end points were changes in the motor and cognitive components of the Functional Independence Measure (FIM) between admission and 3 to 4 months after discharge from IPR and in the National Institutes of Health Stroke Scale (NIHSS) between enrollment and 90 days.

Diagnosis of obstructive sleep apnea (OSA)

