recovery and met with a clinical psychologist for motivational interviewing (MI) during IPR to discuss patients' readiness to change, confidence in using CPAP and coping techniques to adjust to CPAP use (see Table II). The 30-minute face-to-face MI sessions occurred within one week of starting auto-adjusting CPAP. The MI session were focused on building motivation to use CPAP and alter the subject's decisional balance about using CPAP as it relates to patient-specific goals. To improve support, the adherence program included nightly visits by respiratory therapists during IPR to improve self-efficacy with CPAP and tailored written feedback prior to discharge from the IPR unit detailing CPAP download data, adjustments made during IPR and goals and barriers for CPAP use. Phone calls were also made weekly for one month after discharge from the IPR unit to encourage CPAP use and troubleshoot any device or mask problems.

Efficacy Measures

The National Institutes of Health Stroke scale (NIHSS; range, 0 to 42; higher scores indicate greater neurologic impairment) scores were obtained in-person on enrollment and at 90 ± 7 days from enrollment. The Functional Independence measure (FIM) scores were obtained as part of routine clinical care. The FIM included a motor and cognitive component (motor range, 13-91; cognitive range, 5 to 35; lower scores indicate greater functional disability). The admission FIM scores were obtained in-person by rehabilitation nurses and therapists upon admission to the IPR unit and follow-up FIM scores were obtained as part of routine clinical care through phone interview by IT Health Track, Inc., between 3 and 4 months from IPR unit discharge (mean 106 days); telephone response rates are approximately 60%.

Statistical Analyses

We compared baseline demographics, stroke severity and rehabilitation characteristics by adherence, using t-tests and Chi-squared tests as appropriate. To evaluate for predictors of adherence (Table III), we performed logistic regression, adjusting for baseline demographic covariates determined *a priori* including age (≥ 65 years), race/ethnicity (White versus non-White or Hispanic), sex, obesity (body mass index ≥ 30 kg/m²), baseline NIHSS score ≥ 5 and inpatient rehabilitation length of stay (weeks). As those with aphasia were noted to be adherent to CPAP, we added this stroke characteristic into separate models post-hoc.

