We examined for differences in baseline, 3-month and changes between baseline and 3- months in NIHSS, motor FIM and cognitive FIM by CPAP adherence using the t-test with unequal variances (Table IV). We also evaluated for association of CPAP adherence with 3-month NIHSS and cognitive FIM change using linear regression in models adjusting for age ≥ 65 years, sex, race/ethnicity, body mass index ≥ 30 , and baseline NIHSS score at study enrollment (Table IV). Finally, we evaluated the proportion of adherent and non-adherent participants who had improvement in the cognitive FIM and NIHSS, which was greater than the mean improvement among the entire sample: ≥ 7 for cognitive FIM improvement and ≥ 4 for NIHSS improvement (Table V).

Table I. Main Selection Criteria

Inclusion Criteria

Informed consent

Acute ischemic stroke or intraparenchymal hemorrhage

Age \geq 18 years

Admission to inpatient stroke rehabilitation unit at Harborview Medical Center and the University of Washington Medical Center

Exclusion Criteria

Stroke related to bleeding disorder, substance abuse, tumor, vascular malformation, trauma or other secondary cause

Active CPAP use at time of enrollment

Advanced congestive heart failure (New York Heart Association class 3 or 4)

Requiring supplemental oxygen or nasogastric feeding tube

Participation in another research outcome study

Table II. Motivational Interviewing Data Form

Subject's understanding of stroke and sleep apnea:

- Subject's readiness to change:
- □Pre-contemplation
- □Contemplation
- □Preparation
- \Box Action
- □Maintenance

Any small achievable subgoals:

 \Box YES \Box NO

Subject's reason for using CPAP:

□Stroke prevention

□Stroke recovery

□Sleep improvement

 $\Box Other$

Subject's reason for not using CPAP:

□Claustrophobia

□Anxiety

□Sleep disturbance

 \Box Mask fit or leak problems

□Device problems

 $\Box Other$

On a scale of 1-10, how important do you think it is for you to treat sleep apnea and use the

CPAP device?

On a scale of 1-10, how confident are you in your ability to use the CPAP device from now until the next time we meet?

Table III. Baseline factors associated with 3-month CPAP adherence, odds ratio (95% confidence interval)*

*All models included age, sex, obesity and weeks on inpatient rehabilitation. Model 1 additionally included race and baseline NIHSS \geq 5; model 2 for race and aphasia; model 3 for race, aphasia and baseline NIHSS \geq 5.

	Model 1	Model 2	Model 3

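### Table IV relates NIHSS change to adherence measured over nearly the same interval and adjusts only for baseline covariates, so it cannot fully separate CPAP aiding recovery from recovery aiding CPAP use; an exploratory early-use, own-baseline column would help

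*Combined protocol and SAP*

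**What the plan says.** - **Exposure.** Methods: "The primary end point was CPAP adherence over 90 days from CPAP initiation". A patient is adherent with at least 4 hours of use on at least 70% of days, so the full classification is complete only at the end of that period.
- **NIHSS.** Efficacy Measures: the scores "scores were obtained in-person on enrollment and at 90 ± 7 days from enrollment". No intermediate score is described.
- **FIM.** "The admission FIM scores were obtained in-person by rehabilitation nurses and therapists upon admission to the IPR unit", which is before CPAP. The follow-up score comes from a telephone interview "between 3 and 4 months from IPR unit discharge (mean 106 days").
- **Analysis.** Changes are compared "by CPAP adherence using the t-test with unequal variances (Table IV"), and then "We also evaluated for association of CPAP adherence with 3-month NIHSS and cognitive FIM change using linear regression". The adjustment set is age, sex, race/ethnicity, body mass index and baseline NIHSS. Baseline cognitive FIM is not in it. Table V uses the same adherence classification.
- **Use data.** Methods: "Devices were interrogated for nightly usage, average pressure, and a residual apnea-hypopnea index". This sentence concerns the run-in, but the 90-day definition itself requires daily use.

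No early-use, landmark, lagged or time-varying exposure analysis is planned or reported.

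**The concern.** A patient who recovers well may find the mask and device easier to manage once the nightly inpatient therapist visits have ended, and so be more likely to reach 70% of days. Recovery during follow-up would then help to determine the exposure. Because this arises after baseline, adjustment for baseline variables can reduce it but cannot be relied on to remove it.

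Stroke outcome is a stated objective, and NIHSS and FIM change are listed as secondary efficacy end points. With a single arm, adherent versus non-adherent is the only outcome comparison available. At stake is whether the NIHSS (P=0.003 unadjusted, 0.03 adjusted) and cognitive FIM (0.03, 0.02) results are read as a benefit of CPAP.

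**Working it through.** **1. Windows.**
- NIHSS: CPAP starts at or after enrollment, so day 90 of use falls on or after day 90 from enrollment. The earliest permitted visit is day 90 − 7 = 83. At least 90 − 83 = 7 days of classifying use can then follow the outcome.
- FIM: the change starts before CPAP and ends on average 106 days after discharge. If the 3-night run-in starts the clock, at least 106 + 3 − 90 = 19 days before the mean call date lie outside the adherence window. If the clock starts after the run-in, the figure is at least 16. This is a mismatch of windows, not reverse causation in itself.

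**2. Table IV reproduced.** Welch t = (m1 − m2)/√(s1²/n1 + s2²/n2).
- NIHSS: (−3.8 + 1.6)/√(2.6²/30 + 2.2²/19) = −3.18, p=0.0028 (printed 0.003).
- Cognitive FIM: (8.2 − 4.6)/√(6.5²/22 + 3.0²/12) = 2.20, p=0.035 (printed 0.03).
- Motor FIM: p=0.845 (printed 0.83).

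These agree within rounding, so the issue is interpretation and not arithmetic.

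**3. Baseline imbalance.** The same test applied to the scores themselves:

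| | Baseline, adherent vs not | p | 3 months | p |
|---|---|---|---|---|
| NIHSS | 6.5 vs 4.1 | 0.014 | 2.7 vs 2.6 | 0.90 |
| Cognitive FIM | 24.1 vs 28.5 | 0.024 | 32.4 vs 33.1 | 0.51 |

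An analysis adjusted for own baseline can be rebuilt from the printed SDs. Within-group covariance = (SD_base² + SD_3m² − SD_change²)/2, and the pooled slope = Σ(n−1)cov / Σ(n−1)SD_base².
- NIHSS: covariances 10.67 and 3.38; slope (29×10.67 + 18×3.38)/(29×4.3² + 18×2.2²) = 0.594. Difference = 0.1 − 0.594×2.4 = −1.33 (95% CI −2.56 to −0.10, p=0.035), close to the printed adjusted 0.03.
- Cognitive FIM: covariances 9.525 and 5.985; slope (21×9.525 + 11×5.985)/(21×6.9² + 11×3.9²) = 0.228. Difference = −0.7 + 0.228×4.4 = +0.30 (95% CI −2.08 to 2.68, p=0.80), against a printed adjusted 0.02 from a model without baseline cognitive FIM.

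These rebuilt models contain own baseline only, not the other covariates.

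**4. Illustration with no CPAP effect.** All inputs are assumptions except n=49 and the target of about 62% adherent (30/49 = 61%). Recoverable deficit R ~ N(2.9, SD 2.0), recovered as R(1 − exp(−t/30)). Logit of nightly use = N(1.3, SD 1.5) + b(R − 2.9)(1 − exp(−t/30)). Adherent means at least 70% of nights in the window. Residual SD of the change is 1.3. The observed raw gap is 2.2 points.

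| b (log-odds per point) | 90-day, unadjusted: gap, % with p<0.05 | Days 1-30, unadjusted | 90-day, baseline-adjusted* |
|---|---|---|---|
| 0 | 0.0, about 5% | 0.0, about 5% | – |
| 0.2 | 0.5, 11% | 0.3, 8% | 0.19, 7% |
| 0.3 | 0.8, 21% | 0.5, 10% | 0.29, 8% |
| 0.5 | 1.3, 48% | 0.7, 18% | 0.49, 15% |

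*With a baseline-improvement correlation of about 0.67. Table IV's SDs imply, by (SD_base² − cov)/(SD_base × SD_change), 7.82/11.18 = 0.70 in adherent and 1.46/4.84 = 0.30 in non-adherent patients, about 0.60 pooled. A weaker correlation would remove less.

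Per SD of recovery these links are 0.4, 0.6 and 1.0 (b × 2.0). A second model, with links reaching 0.6, 1.2 and 1.8 per SD and no residual noise, gave 27%, 77% and 97%. The rate follows the assumed link, and the documents give nothing from which to estimate that link.

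**The case against.** A reader might infer that a significant Table IV result is what reverse causation alone would produce. The documents do not support this. At the links tabulated above, significance occurs in a minority of unadjusted trials, the largest spurious gap is 1.3 points against 2.2 observed, and baseline adjustment lowers both. Stronger links would raise the rate, but none is documented.

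The printed data also sit awkwardly with the mechanism. Adherent patients are not less impaired at either assessment. Motor FIM, the score closest to handling a device, changes equally (31.2 vs 30.2, P=0.83). Table III links baseline NIHSS of 5 or more (OR 14.9, model 1) and aphasia (OR 12.9, model 2) to more adherence. Baseline imbalance, with regression to the mean or a ceiling (cognitive FIM maximum 35), is a simpler account, especially for cognitive FIM. All of this stands, and it is why the point is that the direction is unresolved, not that reverse causation has been found.

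A reader might also take exposure and outcome to span the same 90 days throughout. That is nearly so for NIHSS and not so for FIM.

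Against the remedy: recovery during days 1-30 stays in the outcome (63% of it under the assumed time constant, 1 − exp(−1)), and early nights are partly supervised inpatient nights. Both are fair. They limit what the early-use column can show but do not make it uninformative.

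Finally, the text speaks of association. That is correct wording, but the outcomes are presented as efficacy end points and no caution on direction is given.

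**Conclusion.** The point holds in this limited form. For NIHSS, the exposure is fixed over nearly the period in which the outcome accrues, at least a week of it can follow the visit, and only baseline covariates are adjusted for. Table IV therefore cannot fully separate the two directions. For FIM, the outcome window overlaps or encloses the adherence window, and the cognitive FIM model lacks its own baseline. With that baseline alone in the model, the difference is about 0.3 points and compatible with none.

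The size of any reverse-causation bias in this trial is unknown. The 11% to 48% range, and 7% to 15% after adjustment, rest on assumed links and an assumed recovery curve. They show that the bias can matter, not that it occurred. The printed P-values reproduce, and the primary end point is unaffected. The analysis should be strengthened, but nothing here invalidates the adherence result.

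**What to change.** Keep the primary end point and the 90-day result. Then:

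1. Add to Table IV a column labelled exploratory sensitivity, with use over days 1-30 from CPAP initiation as the exposure.
2. Adjust each model for that outcome's own baseline score: baseline NIHSS for NIHSS and baseline cognitive FIM for cognitive FIM.
3. In the 90-day NIHSS analysis, count use only up to each patient's NIHSS date. This is a small correction.
4. Report estimates with confidence intervals side by side.
5. State that Table IV is an association that cannot establish direction. Attenuation with early use would be compatible with reverse causation, but also with less exposure captured or with imprecision at n=49 (NIHSS) and n=34 (FIM).

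The cost is one extra set of models on daily use data that the 90-day definition already requires; no new data are collected. The downsides are lower precision, less exposure captured, an early window that includes supervised inpatient use, and only partial removal of the bias (roughly 40-45% of the spurious gap in the simulation). Confounding by motivation or severity would remain.

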White race	10.9 (1.7, 701)	3.7 (0.7, 19.8)	8.2 (1.1, 62.3)
Aphasia		12.9 (1.3, 129)	8.0 (0.7, 87.7)
NIHSS≥5	14.9 (1.9, 115.7)		10.6 (1.2, 92.6)

	Adherent, mean (SD)		Non-adherent, mean (SD)			P-value*		
	Baseline	3-months	Change	Baseline	3-months	Change	Unadjusted	Adjusted
Motor FIM†	48.5 (11.2)	79.7 (12.1)	31.2 (15.7)	47.3 (17.6)	77.5 (10.8)	30.2 (13.2)	0.83	0.65
Cognitive FIM†	24.1 (6.9)	32.4 (3.7)	8.2 (6.5)	28.5 (3.9)	33.1 (2.4)	4.6 (3.0)	0.03	0.02
NIHSS ‡	6.5 (4.3)	2.7 (3.1)	-3.8 (2.6)	4.1 (2.2)	2.6 (2.6)	-1.6 (2.2)	0.003	0.03

Table IV. Improvement in cognitive FIM and NIHSS associated with CPAP adherence

CPAP indicates continuous positive airway pressure; SD, standard deviation; NIHSS, National Institutes of Health Stroke Scale; Cognitive FIM, cognitive component of Functional Independence measure

* Difference between mean changes in outcome between adherent and non-adherent patients: unadjusted using t-test with unequal variances and adjusted for age, sex, body mass index, race and baseline NIHSS using linear regression

† n=22 adherent group and n=12 non-adherent

‡ n=30 adherent group and n=19 non-adherent

Table V. Improvement in cognitive FIM and NIHSS associated with CPAP adherence

Patient characteristics	Adherent	Non-adherent	P -value
Cognitive FIM improvement ≥ 7, n (%)*	10 (45)	3 (25)	0.24
NIHSS improvement \geq 4, n (%) [†]	16 (53)	3 (16)	0.01

* n=22 adherent group and n=12 non-adherent

† n=30 adherent group and n=19 non-adherent

REFERENCES

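### Neither cognitive FIM change analysis includes baseline cognitive FIM, although adherers started 4.4 points lower on a scale capped at 35; that gap could account for most of the 3.6-point difference in gain.

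*Combined protocol and SAP*

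**What the plan says.** Cognitive FIM change is part of a secondary efficacy endpoint. Under Efficacy Measures the scale is bounded ("cognitive range, 5 to 35; lower scores indicate greater functional disability"). The admission score is taken on entry to the rehabilitation unit and the follow-up score by telephone 3 to 4 months after discharge.

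Statistical Analyses describes two comparisons of change between adherence groups. The first is made "by CPAP adherence using the t-test with unequal variances (Table IV"). The second is a linear regression, one of the "models adjusting for age ≥ 65 years, sex, race/ethnicity, body mass index ≥ 30 , and baseline NIHSS score at study enrollment". The Table IV footnote gives the same list: "adjusted for age, sex, body mass index, race and baseline NIHSS using linear regression". Baseline cognitive FIM appears in neither list.

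The cognitive FIM row rests on "n=22 adherent group and n=12 non-adherent" patients. Table IV prints P=0.03 unadjusted and P=0.02 adjusted, but no adjusted coefficient or confidence interval. Table V adds a responder comparison, "Cognitive FIM improvement ≥ 7": 45% vs 25%, P=0.24.

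**The concern.** Adherence was not randomised; patients sorted themselves into the two groups. Their admission cognitive scores differ, and on a bounded scale a lower start leaves more room to rise. Regression to the mean acts in the same direction. A t-test on change removes the starting score correctly only if the 3-month score rises one point for each baseline point, and Table IV implies a much flatter slope.

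Baseline NIHSS does not fill the gap, because it is the starting value of a different scale. It does mean that the NIHSS regression contains the baseline of its own outcome, while the cognitive FIM regression does not.

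At stake is the cognitive half of Table IV's claim that improvement is associated with adherence: a reader would take an association for cognitive benefit that may come mainly from unequal starting points.

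**Working it through.** **Inputs** (Table IV, cognitive FIM; cap of 35 from Efficacy Measures)

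| | Adherent (n=22) | Non-adherent (n=12) |
|---|---|---|
| Baseline mean (SD) | 24.1 (6.9) | 28.5 (3.9) |
| 3-month mean (SD) | 32.4 (3.7) | 33.1 (2.4) |
| Change mean (SD) | 8.2 (6.5) | 4.6 (3.0) |

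**1. Reproduce the printed unadjusted result.** Difference in change = 8.2 - 4.6 = 3.6. SE = sqrt(6.5²/22 + 3.0²/12) = 1.63, t = 2.20, 95% CI 0.3 to 6.9, P=0.035. The printed 0.03 is within rounding of the table entries. The adjusted P=0.02 cannot be reproduced without patient data.

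**2. Compare start and finish.** Baseline: 24.1 - 28.5 = -4.4, Welch P=0.024. Three months: 32.4 - 33.1 = -0.7, Welch P=0.51.

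**3. Room to the cap.** Adherent: 35 - 24.1 = 10.9. Non-adherent: 35 - 28.5 = 6.5. Even if every non-adherer had reached 35, their mean gain would have been 6.5, below the adherers' 8.2. The groups gained 8.2/10.9 = 75% and 4.6/6.5 = 71% of the room they had.

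**4. Slope of 3-month score on baseline.** Within each group, covariance = (SD_baseline² + SD_3-month² - SD_change²)/2.
- Adherent: (47.61 + 13.69 - 42.25)/2 = 9.53; slope 9.53/47.61 = 0.200.
- Non-adherent: (15.21 + 5.76 - 9.00)/2 = 5.98; slope 5.98/15.21 = 0.393.
- Pooled: (21×9.525 + 11×5.985)/(21×47.61 + 11×15.21) = 265.86/1167.12 = 0.228.

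**5. Baseline-adjusted difference.** (32.4 - 33.1) - 0.228×(24.1 - 28.5) = -0.7 + 1.00 = 0.30. Residual SD is 3.06. SE = 3.06×sqrt(1/22 + 1/12 + 4.4²/1167.12) = 1.17 on 31 df, so the 95% CI is -2.1 to 2.7 and P=0.80. Starting from the printed change difference of 3.6 gives 0.20 (P about 0.86); the two versions differ only through rounding in the table. The gap alone predicts (1 - 0.228)×4.4 = 3.40 points of extra gain with no adherence effect.

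**6. Sensitivity.**
- *Rounding:* moving all ten entries by ±0.05 in every combination gives 0.11 to 0.50 (P 0.67 to 0.93).
- *Separate slopes and residual variances by group:* 1.0 at a baseline of 24.1 (95% CI -1.3 to 3.4) and 0.2 at 28.5 (-2.0 to 2.3).
- *Measurement error in baseline:* the documents give no reliability. Assuming 0.8 or 0.6 and dividing the pooled slope by it gives 0.55 or 0.97. Applied to the non-adherent slope at a baseline of 24.1, the same assumptions give 1.5 or 2.2.
- *Slope at which the gap explains half of 3.6:* 1 - 1.8/4.4 = 0.59, above both group slopes.

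**7. What this does to the t-test.** Simulated trials (20,000 per scenario, n=22 and 12) gave both groups the same 3-month law, so adherence had no effect, and Table IV's baseline gap. The mean change difference was 3.3 to 3.4 points and the Welch test gave P<0.05 in 44 to 45% of trials, against 5% with equal baselines. Baseline-adjusted regression rejected in 3 to 5%. The scenarios used normal baselines without a cap, and truncated-normal and beta-shaped baselines with a cap at 35; these shapes are assumptions.

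**8. Could the other covariates restore the result?** With seven terms, 34 - 8 = 26 df remain. At the same SE, P<0.05 needs an estimate of 2.056×1.167 = 2.40 points, so the other five covariates would have to move it from 0.3 to about 2.4.

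**9. Does the method simply erase effects?** Applied to the NIHSS row (30 vs 19), adjusting only for baseline NIHSS, it gives -1.33 points, P=0.035 (from the rounded change means, -1.23, P=0.051). The printed adjusted P is 0.03. Most of that association remains, so the method does not remove differences as a matter of course.

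**The case against.** The 3.6 points is the unadjusted difference only. The coefficient behind P=0.02 is not printed, and the existing covariates moved P from 0.03 to 0.02 rather than weakening the result. The share of the adjusted association due to the baseline gap is therefore unknown. That stands, and it limits how firmly the size can be stated.

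The 0.3 also assumes a common slope and equal residual variance, while the implied slopes are 0.20 and 0.39 and the residual SDs about 3.5 and 1.9. Combining the non-adherent slope with an assumed reliability of 0.6 leaves 2.2 points, most of the 3.6. That is an extreme combination; the other cases examined leave 1.5 points or less.

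The simulations are not independent evidence. The uncapped one returns 3.40 by algebra, and the capped ones are fitted to the same table. What they add is the false-positive rate that the gap produces. Table V is weak corroboration: it points the same way as Table IV, has 13 responders among 34 patients, and shares the headroom limit.

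The most substantive objection is that, in non-randomised groups, change-score and baseline-adjusted analyses answer different questions, and the document uses the language of association. That is true, and the report should say which question it answers. It does not rescue the change-score result as evidence about adherence, because the admission score was taken before CPAP adherence. It can confound the comparison but cannot be a consequence of adherence.

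Table IV does show both baseline and 3-month means, so the imbalance is visible. Displaying it does not adjust for it.

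**Conclusion.** The concern holds. Baseline cognitive FIM is absent from both analyses, and Table IV's own summaries indicate that the starting gap accounts for about 3.4 of the 3.6-point unadjusted difference. With baseline cognitive FIM held fixed, the difference is about 0.3 points (95% CI -2.1 to 2.7).

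This rests on a linear common slope, equal residual variance and no other covariates. The summaries cannot separate the ceiling from regression to the mean, and they cannot give the result of the full model. Nor does the interval show that adherence has no effect: with 34 patients about 3.4 points are detectable with 80% power.

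The effect is confined to a secondary endpoint. The primary adherence endpoint is untouched, and the adjusted NIHSS analysis already includes its own baseline. This should be fixed, because it probably changes a reported conclusion.

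**What to change.** - Regress 3-month cognitive FIM on adherence, with baseline cognitive FIM added to the listed covariates. Base the conclusion on the estimate and its 95% CI rather than on the change-score P-values.
- Because that model fits seven terms to 34 patients, also report a reduced model with only adherence and baseline cognitive FIM.
- Add a ceiling-aware sensitivity analysis, for example Tobit or ordinal regression.
- State that the groups are not randomised and which question the analysis answers. If the change-score comparison stays in the table, label it as descriptive.
- If the rerun agrees with the figures here, state that the cognitive FIM association is not supported after baseline adjustment, and that the sample does not exclude an effect.

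The cost is one covariate already in the dataset, one rerun and two sensitivity models. Precision will be low with 12 non-adherent patients, and the reported result will probably become less favourable.

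### FIM change spans a length of stay that differs between patients, yet the Table IV models omit length of stay and dichotomise age and BMI, leaving a risk of residual confounding of unknown size and direction

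*Combined protocol and SAP*

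**What the plan says.** **Timing of the outcomes.** The Methods define the FIM endpoints as "changes in the motor and cognitive components of the Functional Independence Measure (FIM) between admission and 3 to 4 months after discharge". Efficacy Measures confirms both ends: "The admission FIM scores were obtained in-person by rehabilitation nurses and therapists upon admission to the IPR unit", and follow-up by telephone "between 3 and 4 months from IPR unit discharge (mean 106 days". NIHSS is timed differently: its "scores were obtained in-person on enrollment and at 90 ± 7 days from enrollment". Table IV puts all three outcomes under one 3-months heading.

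**Covariates.** For the logistic models of adherence, the Statistical Analyses section fixes a covariate list in advance that ends with "inpatient rehabilitation length of stay (weeks". The Table III footnote says that weeks on inpatient rehabilitation were in every model. For NIHSS and cognitive FIM change, the same section specifies linear "models adjusting for age ≥ 65 years, sex, race/ethnicity, body mass index ≥ 30 , and baseline NIHSS score at study enrollment". The Table IV footnote gives the same five covariates without cut-points for age or BMI. Neither place lists length of stay or gives a reason for leaving it out.

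**The concern.** Two patients with the same post-discharge call date can have FIM changes measured over different intervals, because the clock starts at admission. A longer stay means more time to recover and more inpatient therapy before the follow-up score. It could also bear on adherence, since the 90-day adherence window opens during the stay and inpatient nights come with therapist visits. If longer-stay patients were both more adherent and more improved for that reason, Table IV would show an association between adherence and FIM change without any effect of CPAP.

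Splitting age at 65 and BMI at 30 adds a smaller problem of the same kind. Each split removes only the between-category part of any confounding, although the underlying values must have been available to form the categories.

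At stake is cognitive FIM, one of the two outcomes in Table IV with a favourable P-value. The interval argument applies to the FIM rows only. The coding of age and BMI affects every adjusted row.

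**Working it through.** **Inputs.** From Table IV: cognitive FIM change 8.2 (SD 6.5), n = 22 adherent; 4.6 (SD 3.0), n = 12 non-adherent; unadjusted P 0.03, adjusted P 0.02. From Efficacy Measures: mean 106 days from discharge to FIM follow-up. Length of stay is not reported, overall or by adherence group, so 1–5 weeks is assumed below.

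**1. The plan's own figure.** For the unequal-variance t-test:
- Difference = 8.2 − 4.6 = 3.6.
- SE = √(6.5²/22 + 3.0²/12) = √(1.920 + 0.750) = 1.634.
- t = 3.6/1.634 = 2.20 on 31.4 df, so P = 0.035. This agrees with the stated 0.03 within rounding of the inputs.
- 95% CI 0.27 to 6.93.

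The same method gives P = 0.0028 for NIHSS (stated 0.003) and 0.845 for motor FIM (stated 0.83). The adjusted results cannot be refitted without patient data.

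**2. Spread of the FIM interval due to length of stay.** Interval = 7w + 106 days for a stay of w weeks.
- w = 1: 113 days.
- w = 5: 141 days.
- Ratio 141/113 = 1.25.

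The NIHSS interval is 83–97 days whatever the stay.

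**3. How much bias would matter.** Bias = (FIM points per extra week) × (difference in mean stay between groups, weeks). Both factors are assumptions. With 0.25–2 points per week and 0.5–2 weeks, the product runs from 0.25 × 0.5 = 0.125 to 2 × 2 = 4.0 points. A bias of 0.27 points towards adherence brings the unadjusted lower limit to zero, for example 1 week at 0.27 points per week. The adjusted result has more room. P = 0.02 on 27 df implies t of about 2.47 against a critical value of 2.05, so with the SE unchanged the estimate would have to shrink by 1 − 2.052/2.473 = 17%.

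**4. What a two-level split leaves behind.** For a normal covariate cut at quantile q, the share of variance kept is φ(z_q)²/[q(1 − q)].
- q = 0.5: 0.637.
- q = 0.4 or 0.6: 0.622.
- q = 0.3 or 0.7: 0.576.

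So 36–42% of any linear confounding stays unadjusted, to the approximation that the covariate is weakly related to adherence. A simulation of 1,000,000 records with a moderate relation (log-odds 0.5 per SD) left 37% for a cut at the median, 44% at 0.5 SD above it and 60% at 1 SD above it.

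**5. Cost in degrees of freedom.** Intercept, adherence and five single-term covariates make 7 parameters.
- FIM: 34 − 7 = 27 residual df, or 26 with length of stay.
- Continuous linear age and BMI replace one binary term each, so they cost none.

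**The case against.** Much of the case on the other side stands.

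- **No link between stay and adherence is shown.** A reader might infer from its place in the Table III models that length of stay is known to be tied to adherence. Naming a covariate in advance is not evidence of association. Table III reports odds ratios only for race, aphasia and NIHSS.
- **The severity route is partly closed.** Adherent patients had worse baseline NIHSS (6.5 against 4.1), which makes longer stays plausible. But baseline NIHSS is already in the Table IV models, so only variation in stay that it does not explain can still confound. Adjustment did not weaken the cognitive FIM result.
- **Motor FIM gives no support.** A longer interval and more therapy should raise motor change too, yet it is 31.2 against 30.2. The 95% CI, −9.42 to 11.42, makes this weak evidence either way.
- **The interval spread can be overstated.** A reader might compare a 1-week stay called at day 90 (97 days) with a 5-week stay called at day 120 (155 days) and get 1.6-fold. Of those 58 days, 30 come from the call window, which adjusting for length of stay would not remove.
- **Length of stay is not a clean baseline covariate.** CPAP starts during the stay, and discharge timing may respond to recovery. Conditioning on it can introduce bias as well as remove it.
- **A visible imbalance may matter more.** Baseline cognitive FIM is 24.1 against 28.5 on a scale capped at 35, with 3-month means of 32.4 and 33.1, and it is not a listed covariate. That is an additional problem and does not answer this one.

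These points argue against making length of stay a primary covariate. They do not argue against continuous age and BMI, a sensitivity model or a correct label.

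**Conclusion.** The point holds as a risk of residual confounding, not as a demonstrated bias. Three things are established from the documents: the FIM interval includes length of stay while the NIHSS interval does not; the Table IV models omit length of stay without explanation; and the text dichotomises age and BMI where the footnote is silent on coding.

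A reader might go further and conclude that length of stay explains the cognitive FIM association. The documents do not support that. They give no length of stay by group, no odds ratio for it and no adjusted estimate with its interval, so neither size nor direction can be stated.

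The 1.25-fold spread rests on the assumed 1–5 weeks. The 36–42% is a share of whatever linear confounding by age or BMI exists, which could be none. It assumes normality and cuts between the 30th and 70th percentiles, and where 65 years and BMI 30 fall is not given. The reason to act is that the unadjusted lower limit is only 0.27 points from zero, in an observational comparison of 34 patients, and the checks need no new data.

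**What to change.** 1. Enter age and BMI as continuous linear terms in all Table IV models, and make the Statistical Analyses text and the Table IV footnote state the same coding. Cost: no degrees of freedom.
2. Keep the FIM model without length of stay as the main adjusted analysis. Add a sensitivity analysis with length of stay in weeks, as used in Table III, and report both estimates with confidence intervals. State that length of stay is partly determined after CPAP starts, so neither model is free of bias. Cost: one degree of freedom (27 to 26 at n = 34). With 12 non-adherent patients, both fits will be imprecise.
3. Label the FIM follow-up in Table IV as admission to 3–4 months after discharge, and keep the 90-day label for NIHSS only.

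All three need only a rerun and an edit on data already held. Reporting length of stay by adherence group alongside would let readers judge how much the sensitivity analysis matters.
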